The VFSS is considered the "gold standard" in the US for diagnosing the nature and severity of dysphagia as well as providing feedback on the effects of dysphagia therapy²¹. Hence, it would not be unusual for a dysphagic patient to undergo at least two VFSS studies over the course of being treated for dysphagia after stroke. The investigational protocol specifies two VFSS assessments be performed within a 1-week period to standardize baseline measures and to provide feedback on the dysphagia treatment under investigation shortly after the intervention. Patients typically undergo a non-instrumented dysphagia assessment before referral for an instrumented VFSS. Participating sites will be instructed to use the study-specific VFSS protocol for patients referred to an instrumented dysphagia assessment if they also appear to meet the rest of the study inclusion/exclusion criteria. Patients meeting the study criteria will require one subsequent VFSS performed according to the study-specific VFSS protocol. Hence, patients will be exposed to one, and possibly two, more VFSS than they would if they were not enrolled in this study.

The VFSS imparts a small dose of ionizing radiation. Zammit-Maempel et. al., reported a median exposure time of 171 seconds and an associated dose of 0.20 milliSieverts or mSv⁴³, while Moro and Cazzani reported a median exposure time of 149 seconds and

CONFIDENTIAL Page 26 of 71

an associated dose of $0.35~\text{mSv}^{44}$. The standardized VFSS protocol proposed for this study is associated with an average duration of 2.9 minutes radiation exposure (95% confidence interval 2.8-3.0 minutes). Extrapolating from the relationship Moro and Cazzani published, the VFSS time of 2.9 min (174 sec), relates to an effective dose of $\sim 0.44 \text{mSv}^{45}$.

Table 1 provides background information on relative average absorbed doses of ionizing radiation that a person would experience when exposed to various sources. On average, a U.S. resident receives an annual radiation exposure from natural sources of about 3.1 mSv. In addition, man-made sources of radiation from medical, commercial and industrial activities contribute roughly 3.1 mSv more to our annual exposure⁴⁶. Computed tomography (CT) scans, are among the largest of these sources, with a head CT contributing 2mSv⁴⁷.

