5 STUDY POPULATION

5.1 INCLUSION CRITERIA

CONFIDENTIAL Page 34 of 71

To be eligible to participate in this study, an individual must meet all of the following criteria:

- 1. Age \geq 18 and \leq 90 years.
- 2. Acute ischemic or hemorrhagic cerebral stroke within 7-28 days of baseline VFSS.
- 3. Score of 0 or 1 on NIHSS question 1a, Level of Consciousness.
- 4. *Moderate to severe dysphagia (PAS ≥4) on baseline VFSS (Baseline VFSS must meet the threshold criteria of demonstrating a PAS of ≥ 4, in three of the six boli (5 mL/1 tsp/bolus), during swallowing "thin liquid" barium media as assessed by the clinical staff administering the VFSS) unless its deemed too high risk then only 2 swallows will qualify.
- 5. Willing and able to have the Phagenyx® Catheter placed transnasally.
- 6. Willing and able to provide informed consent.
- 7. Stated willingness to comply with all study procedures and availability for the duration of the study.

*Note that the baseline VFSS will include testing with both thin liquids (up to 6 swallows) and nectar liquids (up to 6 swallows). For inclusion criterion 4, only the thin liquid swallows on the baseline VFSS will be considered. However, for descriptive statistics and other analyses, both the thin liquid and nectar liquid swallows on the VFSS will be considered.

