7 VFSS STOPPING CRITERIA AND PATIENT/SITE/STUDY TERMINATION

7.1 VFSS STOPPING CRITERIA

• If the PAS is ≥ 6 (see below) for three consecutive bolus trials of the same consistency, that consistency should be stopped and the investigator (or trained and authorized designee) can decide if it is safe to move to the next consistency to assess dietary modification, or if the study needs to be stopped.

Penetration Aspiration Score Definitions:

- Score = 6: Material enters the airway, passes below the vocal folds and is ejected into the larynx or out of the airway.
- Score = 7: Material enters the airway, passes below the vocal folds & is not ejected from the trachea despite effort
- Score = 8: Material enters the airway, passes below the vocal folds & no effort is made to eject
- A 'Stop' may be applied at any time if the Investigator (or trained and authorized designee) feels it is unsafe for the patient to continue.
- If VFSS time exceeds 3 minutes, the procedure must be stopped.

Regardless of completion of the PES treatment, patients will be encouraged to remain in the study until they have completed the protocol-required follow-up period while maintaining respect for all patient rights. Patients are free to withdraw from participation in the study at any time upon request.

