4.8. Efficacy Evaluation

4.6.1 Primary Efficacy Analysis

The primary endpoint is trichotomized PAS on each bolus, determined by VFSS 48 hours (+/- 24 hours) after completion of PES treatment. The three ordinal PAS categories are defined as Safe (PAS 1-3), Penetration (PAS 4-5), and Aspiration (PAS 6-8). Each patient contributes 12 measurements to the primary endpoint, of which six are from boli of a thin consistency and 6 are from boli of a nectar consistency.

The ITT population will be used for the primary analysis.

A cumulative logistic model will be used to analyze the primary endpoint, and a sandwich variance estimator via a generalized estimating equations approach will be used to account for correlated PAS outcomes within each patient.

The statistical model for the primary analysis will include treatment, bolus consistency, baseline maximum PAS, and treatment by consistency interaction as predictors. The response of individual i on bolus t is coded as $y_{it} = 1$ for a safe swallow, $y_{it} = 2$ for a swallow resulting in penetration, and $y_{it} = 3$ for a swallow resulting in aspiration. The log odds of a swallow with response $\leq j$ conditional on predictors x_{it} is modeled as

$$logit(P(y_{it} \le j | x_{it}))$$

$$= \beta_j + \beta_{base} * base_{it} + \beta_{trt} * trt_i + \beta_{nectar} * nectar_t + \beta_{trt*nectar} trt_i * nectar_t$$

with ordered intercept terms $\beta_1 < \beta_2$, a treatment indicator trt_i (1=PES, 0=control), and a consistency indicator $nectar_i$ (1=nectar, 0=thin). The maximum PAS (1-8) of individual i across all pre-treatment swallows of a given consistency at baseline is denoted $base_{it}$. The GEE approach with robust sandwich estimator is used to account for within subject correlation.

Missing PAS data will be imputed in the primary analysis. PAS values that are missing due to application of VFSS stopping criteria will be assigned the worst (highest) post-treatment PAS value. For patients who have no post-treatment PAS data due to lost-to-follow-up or death, the post-treatment PAS values will be imputed from baseline PAS values and other patient baseline characteristics using multiple imputation. In addition, tipping point analysis will be performed as a sensitivity analysis.

The estimated treatment effect in the logistic model will be presented along with standard error. The treatment effect will also be presented as an odds ratio with 95% confidence interval.

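### The primary model adjusts for a consistency-specific maximum baseline PAS, which discards most of the baseline information and has no value on nectar rows when the baseline exam ended before nectar

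*SAP*

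**What the plan says.** SAP 4.6.1 lists the model terms: "The statistical model for the primary analysis will include treatment, bolus consistency, baseline maximum PAS, and treatment by consistency interaction as predictors". The covariate is the maximum PAS (1-8) "across all pre-treatment swallows of a given consistency at baseline", entered as a single linear term. A thin row therefore carries the thin maximum and a nectar row the nectar maximum.

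Protocol 5.1 admits patients "demonstrating a PAS of ≥ 4, in three of the six boli" of thin liquid as read by site staff, "unless its deemed too high risk then only 2 swallows will qualify". It adds: "For inclusion criterion 4, only the thin liquid swallows on the baseline VFSS will be considered". The baseline exam allows up to six swallows of each consistency and sets no minimum for nectar.

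Protocol 8.1.3 lists thin first. Under Protocol 7.1, three consecutive scores of 6 or more end that consistency, and the investigator then chooses between moving to the next consistency and ending the exam. The investigator may also stop at any time. A further rule reads: "If VFSS time exceeds 3 minutes, the procedure must be stopped".

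SAP 4.6.1 has two imputation rules, one for boli lost to the stopping criteria and one for patients with no follow-up exam. Both assign post-treatment values. SAP 4.3.8 says that, in general, missing data points are not substituted.

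**The concern.** The endpoint is scored bolus by bolus, so what predicts it is how often a patient swallows unsafely. The maximum does not record this: a patient unsafe on three of six thin boli can have the same value as one unsafe on all six. Up to 12 baseline boli are scored, and each row is adjusted for one extreme value.

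Separately, a patient whose baseline exam stopped after thin has no nectar maximum. If nectar is swallowed at follow-up, there are observed primary-endpoint scores with no covariate. The SAP does not say whether those rows are kept, dropped or filled, or whether the whole patient goes. Baseline PAS is also an input to the multiple imputation, so the gap may carry over there. The affected patients tend to be the most severe. The SAP also does not say whether the covariate is the site or the core-lab reading.

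**Working it through.** **The plan's own figure.** The documents attach no number to the covariate. The nearest is 95% power for the primary endpoint at an odds ratio of 2.23 (SAP 4.2), from simulations whose inputs are not given. It can be bracketed with the proportional-odds variance 12/[N_eff(1 − Σp̄³)], where p̄ are the mean category shares and N_eff = 180 × 12/(1 + 11 × ICC). This assumes 1:1 allocation and the final boundary 1.9929 from SAP 4.5.3. N_eff is 2160/3.2 = 675 at ICC 0.2 and 2160/9.8 = 220 at ICC 0.8. Power runs from over 99% down to 78%, and 95% fits an ICC of about 0.4-0.6. The figure is neither confirmed nor refuted.

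**Step 1: crowding of the thin maximum.** Entry fixes a lower limit of 4 on the site reading. Suppose a patient has three qualifying boli with scores spread evenly over 4-8.
- Independent boli: P(max = 8) = 1 − 0.8³ = 49%; P(max ≥ 6) = 1 − 0.4³ = 94%.
- Fully dependent boli: 20% and 60%.

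Simulated eligible patients, with the 3-of-6 entry rule and latent between-patient SD of 1 to 3:

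| Assumed PAS mix | Thin max = 8 | Thin max ≥ 6 | Nectar max = 8 | Thin stopping rule met |
|---|---|---|---|---|
| Mostly penetration | 32-41% | 75-84% | 17-20% | 9-25% |
| Mixed | 65-78% | 93-97% | 44-48% | 26-47% |
| Mostly aspiration | 84-93% | 99-100% | 65-69% | 46-64% |

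Across all settings tried, the share with a thin maximum of 8 was roughly 25-93%.

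**Step 2: precision lost.** Cumulative-logit GEE (working independence, sandwich variance), N = 180, latent SD 2, 250 runs per setting. Each cell is the thin-bolus coefficient divided by its SE. Because the conditional log odds ratio itself grows with a better covariate, information is compared through z².

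| Mix | No covariate | Maximum | Mean PAS | (z mean / z max)² |
|---|---|---|---|---|
| Mixed | 0.88/0.200 = 4.40 | 0.89/0.197 = 4.52 | 0.95/0.190 = 5.00 | 1.22 |
| Penetration | 0.88/0.206 = 4.27 | 0.92/0.202 = 4.55 | 0.96/0.196 = 4.90 | 1.16 |
| Aspiration | 0.82/0.198 = 4.14 | 0.83/0.196 = 4.23 | 0.90/0.189 = 4.76 | 1.26 |

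In these rows the maximum adds 5-14% to the information of the unadjusted model (for example (4.52/4.40)² = 1.06), while the mean adds 29-32% (for example (5.00/4.40)² = 1.29). Other runs, under different assumed distributions, put the gain of the mean over the maximum at 5-16% and at 9-26%; the latter set found no loss from pooling the consistencies. The overall range of 5-26% corresponds to 0.05 × 180 = 9 up to 0.26 × 180 = 47 patients.

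**Step 3: missing nectar covariate.** At latent SD 2 the thin stopping rule is met at baseline by 18% (penetration), 39% (mixed) or 58% (aspiration) of eligible patients. If the exam then ends in 25-75% of those, the share with no nectar maximum runs from 0.18 × 0.25 ≈ 5% to 0.58 × 0.75 ≈ 43%. Standard errors, complete covariate → after deletion:

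| Setting | No nectar baseline | Thin coefficient, rows dropped | Averaged effect, rows dropped | Thin coefficient, patients dropped |
|---|---|---|---|---|
| Penetration, 25% ended | 5% | 0.202 → 0.202 | 0.193 → 0.195 | 0.202 → 0.207 |
| Mixed, 75% ended | 30% | 0.198 → 0.197 | 0.190 → 0.204 | 0.198 → 0.238 |
| Aspiration, 75% ended | 43% | 0.196 → 0.197 | 0.186 → 0.210 | 0.196 → 0.261 |

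In the worst row, the averaged-effect SE rises by 0.210/0.186 − 1 = 13%. If patients are dropped, the thin SE rises by 0.261/0.196 − 1 = 33%, and simulated power falls from 0.99 to 0.91. The thin coefficient is nearly untouched by row deletion because thin is coded 0 and the model has a treatment-by-consistency interaction, so β_trt is the thin-bolus effect.

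**The case against.** Much of the case on the other side stands, and it rules out several stronger readings.

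- *The entry criterion drives the covariate to its ceiling.* It does not. It sets a floor of 4, on thin only; nectar has no threshold, and its maximum was below 4 in 5-16% of simulated patients. Crowding comes from taking a maximum, and its extent depends on a PAS distribution that the documents do not give.
- *The time limit removes nectar from a third to a half of exams.* Protocol 2.4.1 gives an "average duration of 2.9 minutes radiation exposure". With assumed SDs of 0.25 to 1.5 minutes, 1 − Φ(0.1/SD) puts 34-47% of exams over 3 minutes. But 2.9 minutes is the mean for the whole exam. Overrunning normally trims late nectar boli, and a maximum over those already given still exists. The figure is not evidence of missing nectar.
- *The analysis is then not intention-to-treat.* The population is defined by patient. If only nectar rows go, each patient stays in through the thin rows. Deletion is also a software default that the SAP does not state; 4.6.1 opens by saying missing PAS will be imputed, although its specific rules name only post-treatment values.
- *The result is biased.* A crowded baseline covariate costs precision and does not bias a randomised comparison.

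The two-swallow exception does not say that nectar is skipped, and ending the exam after the thin stopping rule is discretionary. It is also fair that a mean treats an ordinal scale as numeric and that pooling gives up consistency-specific severity. The first applies equally to the maximum, which enters as a linear term. On the second, pooling cost nothing in the runs that tested it.

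**Conclusion.** The point holds in two parts. First, the maximum is an inefficient adjuster for a per-bolus endpoint. In every setting tried a baseline mean did better, by about 5-26% in information. The direction is consistent; the size rests on assumed PAS distributions and within-patient correlation. Simulated power with the complete covariate was 0.99 or higher, above the SAP's 95%, so the gain is best read as information and not as power points for this trial.

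Second, the covariate is undefined on nectar rows for any patient whose baseline exam ended before nectar, and no rule fills it. This follows from the text alone. How many patients are affected cannot be read from the documents (5-43% under the assumptions above). The consequence for the tested coefficient is small if only rows are lost. It is larger for a consistency-averaged effect, and larger again if whole patients are lost. That choice should not be left to software. Both parts are worth settling in the SAP, but neither threatens the validity of the comparison.

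**What to change.** In SAP 4.6.1, define the baseline covariate at patient level as the mean core-lab PAS, or the share of unsafe boli (PAS 4-8), over the available baseline boli. State how baseline boli not given because of the stopping rule are filled. Enter the same value on thin and nectar rows. It then exists for every randomised patient with a baseline VFSS, and no observed follow-up row is lost for want of a covariate. Use the same definition in the imputation model, and align SAP 4.3.4, which says no covariate-adjusted analysis is planned.

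If the maximum is kept, the SAP should at least say what value it takes when a consistency was not given or was cut short, and whose reading it is. In the worst simulated setting, setting the missing nectar maximum to 8 restored the standard errors almost exactly (0.197 against 0.196 for thin, 0.187 against 0.186 averaged). That closes the gap but does not recover the lost precision.

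The cost is SAP wording; no new data are needed, because the core lab already reads the baseline exams (Protocol 4.1). The power simulation may need a rerun. The change should be made before the first unblinded interim analysis, which uses this model.

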9.4.2 ANALYSIS OF THE PRIMARY EFFICACY ENDPOINT

The primary analysis will be performed on the ITT population. The primary endpoint is trichotomized PAS on each bolus, determined by VFSS 48 hours after completion of PES treatment. The three ordinal PAS categories are defined as Safe (PAS 1-3),

CONFIDENTIAL Page 56 of 71

Penetration (PAS 4-5), and Aspiration (PAS 6-8). Each patient contributes 12 measurements to the primary endpoint, of which 6 are from boli of a thin consistency and 6 are from boli of a nectar consistency.

Missing PAS data will be imputed in the primary analysis. PAS values that are missing due to application of VFSS stopping criteria will be assigned the worst (highest) post-treatment PAS value. For patients who have no post-treatment PAS data due to lost-to-follow-up or death, the post-treatment PAS values will be imputed from baseline PAS values and other patient baseline characteristics using multiple imputation. In addition, tipping point analysis will be performed as a sensitivity analysis.

A cumulative logistic model will be used to analyze the primary endpoint, and a sandwich variance estimator via a generalized estimating equations approach will be used to account for correlated PAS outcomes within each patient. Modeling details are specified in the SAP.

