4.3. General Statistical Methods and Data Handling

4.3.1. General Methods

All output will be incorporated into Microsoft Excel or Word files, sorted and labeled according to the International Conference on Harmonisation (ICH) recommendations, and formatted to the appropriate page size(s).

Tabulations will be produced for appropriate demographic, baseline, efficacy and safety parameters. For categorical variables, summary tabulations of the number and percentage within each category (with a category for missing data) of the parameter will be presented. For continuous variables, the mean, median, standard deviation, minimum and maximum values will be presented. Time to event data will be summarized using Kaplan-Meier Methodology using 25th, 50th (median), and 75th percentiles with associated 2-sided 95% confidence intervals, as well as percent of censored observations.

Formal statistical hypothesis testing will be performed on the primary and secondary efficacy endpoints with all tests conducted at the 1-sided, 0.025 level of significance. Summary statistics will be presented, as well as confidence intervals on selected parameters, as described in the sections below.

For all analyses, baseline will be defined as the most recent measurement prior to the date and time of the administration of active treatment with Pharyngeal Electrical Stimulation or a sham treatment. Therefore, baseline may be on the same day as the start of study treatment, but prior to the administration of the study treatment.

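### The primary imputation lists only baseline predictors: treatment arm is missing and nothing keeps a patient's 12 swallows correlated. Both must be fixed together, because adding arm alone would replace attenuation with an understated standard error.

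*SAP*

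**What the plan says.** The primary endpoint is the three-category PAS of each swallow at the 48-hour VFSS. SAP 4.6.1 states: "Each patient contributes 12 measurements to the primary endpoint, of which six are from boli of a thin consistency", with the other six from nectar. The cumulative logit model "will include treatment, bolus consistency, baseline maximum PAS, and treatment by consistency interaction as predictors". For the variance, "The GEE approach with robust sandwich estimator is used to account for within subject correlation".

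Missing swallows are handled in two ways. Where a stopping rule cut the study short, "PAS values that are missing due to application of VFSS stopping criteria will be assigned the worst (highest) post-treatment PAS value". Multiple imputation is kept for a different group, which the SAP introduces with the words "For patients who have no post-treatment PAS data due to lost-to-follow-up or death". The rule for this second group in SAP 4.6.1 is that "the post-treatment PAS values will be imputed from baseline PAS values and other patient baseline characteristics using multiple imputation". Protocol 9.4.2 has the same rule: "imputed from baseline PAS values and other patient baseline characteristics using multiple imputation".

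Neither document names treatment arm as an imputation predictor. Neither says whether the 12 swallows are imputed jointly, sequentially or one at a time. The form of the imputation model, the number of imputations and the combining rule are also not given. A tipping-point analysis and an analysis that ignores missing values are planned as sensitivity analyses.

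**The concern.** The imputed patients lack all 12 swallows, so none of their own post-treatment data can carry the within-patient correlation. It has to come from joint or sequential imputation or from a patient effect, and the text mentions none of these.

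Two separate faults follow if the predictor list is taken at its word and each swallow is drawn on its own.

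- **Arm omitted.** Imputed patients in both arms are drawn from one common distribution given baseline. They carry no treatment difference and dilute the effect.
- **Correlation omitted.** An imputed patient's mean over independently drawn swallows varies far less than an observed patient's. The sandwich estimator sees nearly noise-free clusters, and Rubin's rules cannot restore patient-level variation that was never drawn.

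The first fault masks the second. Someone who notices only that arm is missing, and adds it, turns a mildly conservative test into a liberal one. The Wald statistic concerned is the one that SAP 4.5.1 to 4.5.5 uses for conditional power, the efficacy boundary and the combination test.

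**Working it through.** **1. The plan's own figures.** Enrolment: 180/0.80 = 225, and 270/0.80 = 337.5, rounded up to 338. Boundaries: Lan-DeMets O'Brien-Fleming spending at t = 2/3 is 2[1 − Φ(2.2414/√(2/3))] = 0.00605, so c1 = 2.5093. With correlation √(2/3), c2 = 1.9929 and total error is 0.0250. These reproduce SAP 4.5.3. The 95% power in SAP 4.2 comes from simulation and cannot be rebuilt from the text. Ignoring the interim look, it implies a standard error of about ln(2.23)/(1.9929 + 1.645) = 0.802/3.638 = 0.220.

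**2. Assumptions, not in the documents.** Share of patients with no 48-hour VFSS: 5, 10 or 20%, missing completely at random. Latent ICC: 0.3 or 0.6. The value 0.6 gives a complete-case SE of 0.217 to 0.219, close to 0.220. There is one fixed look, with "all tests conducted at the 1-sided, 0.025 level of significance" as the reference.

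**3. Closed form.** Let f be the fraction imputed, ρ the within-patient correlation, m the swallows behind the coefficient (6 for thin only, which is what the treatment term means with the interaction in the model; 12 for the average), and swallow variance 1. A patient mean has variance V = ρ + (1 − ρ)/m. Variances below share a common factor, which cancels.

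*Arm included, independent draws.* The estimate behaves like complete cases, with true variance V/(1 − f). Rubin's total is T = W + B, with W = (1 − f)V + f/m and B = f/m + f²/[m(1 − f)]. At f = 0.2, ρ = 0.6, m = 6:
- V = 0.6667; W = 0.5333 + 0.0333 = 0.5667; B = 0.0333 + 0.0083 = 0.0417; T = 0.6083.
- True variance = 0.6667/0.8 = 0.8333.
- R = estimated SE / true SD = √(0.6083/0.8333) = 0.854.
- One-sided error = 1 − Φ(1.96 × 0.854) = 0.047.

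Over ρ = 0.3 to 0.7 and m = 6 or 12, error is 0.041 to 0.053 at 20% missing, 0.033 to 0.037 at 10%, and 0.029 to 0.031 at 5%. If the same R applied at both looks, boundaries 2.5093 and 1.9929 would give 0.043 to 0.056 at 20%.

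*Arm omitted, independent draws.* The effect shrinks by about (1 − f). The true variance is (1 − f)V and T = (1 − f)V + 2f/m. At the same values R = √(1 + 0.0667/0.5333) = 1.061, and error = 1 − Φ(1.96 × 1.061) = 0.019.

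**4. Simulation of the SAP model.** Settings: 225 patients, 12 swallows each, cumulative logit with independence working correlation and patient-clustered sandwich, 10 imputations, Rubin's rules, 3000 null trials per row group (Monte Carlo SE about 0.003 to 0.004).

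| ICC, missing | Method | SE / true SD | P(Z>1.96) | P(Z>1.9929) | P(Z>2.5093) |
|---|---|---|---|---|---|
| 0.6, 20% | Complete cases | 0.999 | 0.025 | 0.023 | 0.005 |
| | No arm, independent | 1.069 | 0.020 | 0.018 | 0.003 |
| | Arm, independent | 0.863 | 0.044 | 0.041 | 0.014 |
| | Arm, whole patient | 1.000 | 0.024 | 0.022 | 0.005 |
| 0.3, 20% | Complete cases | 0.991 | 0.028 | 0.027 | 0.006 |
| | No arm, independent | 1.097 | 0.018 | 0.017 | 0.002 |
| | Arm, independent | 0.887 | 0.041 | 0.039 | 0.014 |
| | Arm, whole patient | 0.998 | 0.030 | 0.028 | 0.007 |
| 0.6, 10% | Complete cases | 1.011 | 0.019 | 0.017 | 0.006 |
| | Arm, independent | 0.941 | 0.028 | 0.026 | 0.008 |
| 0.6, 5% | Complete cases | 0.992 | 0.026 | 0.023 | 0.005 |
| | Arm, independent | 0.958 | 0.030 | 0.028 | 0.006 |

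The complete-case rate in the 10% runs is low by chance, so the closed form is the better guide there. Drawing the imputation parameters with a cluster-robust covariance does not cure the problem (0.043 at ICC 0.6, 20%).

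**5. Under the planned effect** (odds ratio 2.23, ICC 0.6, 20% missing, 600 trials, Monte Carlo SE of power about 0.012). The mean log odds ratio is 0.756 with no data missing, 0.753 for complete cases, 0.598 with no arm and independent draws, and 0.745 with arm and whole-patient draws. The ratio 0.598/0.753 = 0.79 matches the predicted 0.8. Power at 1.9929 is 0.928 for complete cases, 0.902 with no arm and 0.908 with whole-patient draws. The clear loss is therefore bias in the estimate; the power differences are small.

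**The case against.** A reader might infer that the primary test as planned has nearly twice its nominal error. The documents do not support that, for four reasons.

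- **Arm is not in the list.** The inflation arises only if arm is added. One cannot read the list strictly to exclude other swallows and then loosely to admit arm. Read strictly throughout, the test is conservative.
- **Independence is not stated.** For patients with no post-treatment data, a joint or chained imputation of all 12 swallows could be described in the same words.
- **The 20% is a different quantity.** SAP 4.2 defines it as dropout to 7-day data. The VFSS is at 48 ± 24 hours, in patients expected to stay for up to two weeks (Protocol 5.4). No rate is given for a missing VFSS, and at 5 to 10% the rise is modest.
- **The interim and combination tests were not simulated.** If stage 1 consists of patients who completed day 7, few should lack the VFSS. An early efficacy stop also needs the secondary endpoint, which is not imputed.

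All four stand, and they limit the claim. They do not remove it: the literal procedure attenuates the effect, and the obvious repair introduces the opposite fault. The planned sensitivity analyses could reveal a discrepancy, but they do not repair the primary test.

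**Conclusion.** The point holds as a fault in how the primary imputation is specified, and it should be corrected before any unblinded analysis. Taken literally with swallow-by-swallow draws, and at an assumed 20% imputed, the rule shrinks the log odds ratio by about a fifth, overstates its SE by 7 to 10% and gives a mildly conservative test. With arm added alone, the SE would be 11 to 14% too small and the test liberal, to a degree that depends on the share imputed. Whole-patient draws with arm remove both problems: one-sided error 0.024 against 0.025 for complete cases at ICC 0.6.

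The sizes rest on the assumed ICC, missing rate and mechanism, and on a single look. They also depend on the final critical value: SAP 4.5.3 gives 1.9929 and SAP 4.5.4 gives 2.5093. At 2.5093 the rejection rate with arm and independent draws is about 0.014, above the nominal 0.0060 for that boundary but below 0.025. The two sections must be reconciled. A contradiction between them is not a safeguard.

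**What to change.** Replace the imputation sentence in SAP 4.6.1 and Protocol 9.4.2 with a specification along these lines:

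- Multiple imputation with treatment arm, baseline PAS by consistency and named baseline covariates as predictors.
- All 12 post-treatment swallows imputed jointly at patient level, by wide-format joint or sequential imputation, or by an ordinal multilevel model with a patient random intercept.
- Number of imputations stated, and results combined by Rubin's rules.
- Imputation run separately for stage 1 and stage 2, so that Z1 and Z2 remain independent as SAP 4.5.5 requires.

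Arm and patient-level draws must be adopted together. State one final critical value in SAP 4.5.3 and 4.5.4.

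The cost is one SAP paragraph, the matching protocol sentence and some programming. The interval will be wider than independent draws would give: mean SE 0.219 against 0.188 at ICC 0.6 and 20% missing. That width is the true uncertainty, and it matches complete cases (0.217).
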